8.0 TOXICITIES/SIDE EFFECTS

There are minimal risks associated with participation in this study. Participants may experience pain undergoing fingerstick blood draw (e.g. soreness at puncture site) and

may experience dizziness or light-headedness. Staff will be trained to conduct fingerstick procedures and trained to identify participant's signs of distress during and after procedures. Participants may on occasion recognize problems or identify unmet clinical needs as a result of participating in a study such as this. If patients do report concerns of study burden, distress or mention specific medical concerns he will be informed to report this concerns to research staff who will be trained to alert study investigators who will make referrals to low cost community health services as appropriate.

9.1 PRIMARY OUTCOMES

The primary outcomes are:

- To collect preliminary data on in-vehicle excess PM exposure the personal DataRam will monitor/report the PM levels as time-averaged sample (hourly averages) that will be monitored at work site and at homes across all groups
- To conduct a preliminary assessment of the correlation between PM exposure and physiologic and biochemical markers associated with increased risk of lung cancer and CVD the personal DataRam will monitor/report PM levels (hourly averages) that will be analyzed in comparison to increased systolic blood pressure, reduced heart rate variability, and presence of biological markers related to lung cancer and CVD risk.

10.0 CRITERIA FOR REMOVAL FROM STUDY

Participants may be removed from the study protocol based on the following circumstances: 1) if they choose to voluntarily withdraw; 2) they are determined to be ineligible for the study; 3) they express significant distress related to completion of the study (the study staff will refer the participant to counseling and support services if needed); or 4) if the PI believes it is in the participant's best interest to do so.

11.0 BIOSTATISTICS

Overview. This pilot study follows a two parallel arm design. Drivers will be randomized to one of two groups, an Intervention Group (an in-vehicle HEPA filter will be provided) and a Wait-list Control Group (HEPA filter will be provided at the end of wait-list period). We plan to recruit a sample of n=14 participants in each group (n=11 per arm with analyzable (non-missing) data, assuming a 25% drop-out rate as described below).

General analytic strategies. The general data analytic paradigm for this pilot study will be descriptive statistics only. The aim is to collect pilot data to help guide a future randomized intervention study. Descriptive statistics and assessments of correlations will be sought to address the aims (see below). The sample size of 14 per condition was primarily determined by resources limitations. A sample of 14 per condition was deemed possible within the funding resources of no more than 2 years.

Analytic plans for the Specific Aims.

Aim 1a: The primary aim will be to collect preliminary data on in-vehicle excess PM exposure.

Descriptive statistics (means and standard deviations) will be sought on: 1) PM size distribution 2) mass concentration, and 3) chemical composition for all three groups. These observations will be used to evaluate to what extent the two groups were exposed to these environmental hazards. For each study participant, an area-under-the-curve (AUC) summary will be sought for each of the three PM measurements over appropriate time periods. Generally, a daily average will be calculated from the hourly PM assessments. Then the AUC of the 28 daily averages will be calculated per person to represent the summary of PM exposures during study participation.

Aim 1b: To conduct a preliminary assessment of the correlation between PM exposure and physiologic and biochemical markers associated with increased risk of lung cancer and/or CVD.

For each group, a correlation matrix will be constructed between the three components of the AUC outcomes described in Aim 1a and a set of physiologic and biochemical markers. Generally, Pearson's correlation coefficients will be sought. If preliminary analyses found the variables to be skewed, then Spearman's rank correlation coefficients will be calculated instead. The purpose of these correlation coefficients are to examine the associations between the environmental exposure to air pollutants and physiologic and biochemical markers. Point-biserial correlation coefficients will be sought between the continuous AUC summaries of PM data and other binary variables of interest (e.g., methylation). These correlation coefficients can be sorted in descending order to help identify the top candidates of physiologic and biochemical markers that are most likely to be associated with PM exposure. Care will be taken to match the variables by time, using the time stamps from the PM measurements and the date of biomarker serum collection. For example, the AUC of PM in the first week will be associated with serum cytokines measured during the first week. This work will have to be done in a post-hoc manner, after we have all data sources. Then we will evaluate the best strategies to link them together by time. It helps to have automatic time stamps by the PM measurement devices, which is likely to minimize coding errors and missing data.

Aim 2: To use a randomized wait-list controlled design to conduct a pilot study of whether a targeted intervention, installation of a portable car high-efficiency particulate air (HEPA) filter (to remove PM), results in a reduction of in-vehicle PM exposure and associated physiologic and biochemical markers among taxi drivers..

We will calculate the difference in the three PM components and in physiologic/biochemical markers between the HEPA intervention condition and the Wait-List Control condition to obtain the pilot data needed for a future, larger study with the potential to provide remediation to potential harmful exposures to air pollution among NYC taxi drivers.

Aim 3: To collect feasibility data on conducting the proposed randomized wait-list controlled pilot study among New York City taxi drivers.

We will perform descriptive statistics to describe the feasibility data collected in this study (number of participants approached, number refused, number dropping out, time and effort required to conduct the study, adherence with the study protocol including carrying dataRAMS to and from home and work and completion of the multiple biological measurements, etc.). These data will inform a future, large-scale randomized controlled study.

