1.0 PROTOCOL SUMMARY AND/OR SCHEMA

New York City (NYC) is home to 100,000 taxi drivers, of whom 92% are immigrants. The overwhelming majority are men. This large, male taxi driver population faces poor health outcomes that can be mitigated through scalable, targeted interventions. NYC taxi drivers work long hours (10-12 h/d shifts, ~6d/wk), most often in heavy traffic. Exposure to high levels of particulate matter (PM) and air pollution are closely linked to lung cancer and cardiovascular disease (CVD).

DRIIVE (Data and Research on Interventions to Improve the Vehicular Environment) is a community-engaged translational pilot project that will utilize a two parallel arm design to obtain preliminary data on associations between Particulate Matter (PM)/air pollution and physiologic measurements and biomarkers in taxi drivers, and to determine the impact of a HEPA filter (to remove PM and volatile organic compounds) intervention on such physiologic measurements and biomarkers. DRIIVE is funded by the New York State Department of Health Empire Clinical Research Investigator Program (ECRIP), which trains physicians in clinical research in New York. Drivers will be randomized to one of two groups: Intervention or Wait-list Control. In total, two groups of 14 participants in each group will be recruited: 1) Wait List Control group, who will receive a HEPA filter at the end of the 1 month participation period and 2) Intervention group, who will receive a HEPA filter two weeks into their participation period. The project will be completed within a 2 year timeframe.

**The HEPA filter intervention depicted above by “...” will be introduced after 2 weeks in the Intervention group, and at the end of the study for the Wait-list control group. PM and biological measurements will be conducted throughout the study in all 2 groups and is depicted above by “—”*

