4.1 OVERVIEW OF STUDY DESIGN/INTERVENTION

4.2 Design

This study is proposed to be carried out across a two year period including an intervention period and dissemination of results to the Taxi Network community. Twenty eight non-smoking male NYC cab drivers will be recruited and randomized to one of two study arms, an Intervention Group (to receive the HEPA filter 2 weeks into their 4 week period of participation) and a Wait-list Control Group (to receive the HEPA filter at the end of their 4 weeks of participation). For the Intervention and Wait-list Control Group drivers, during the first 2 weeks, measurements (e.g. biological markers and air monitoring) will be taken under usual conditions. At the end of the initial two weeks, portable HEPA air purifiers (136) will be placed in the Intervention Group drivers' cars and the air monitoring and biological parameters will be repeated for another 2-week period, to determine changes in PM levels and physiological measurements as a result of this targeted intervention. The Wait-list Control Group drivers will not receive a HEPA air purifier at this time, but will also have the air monitoring and biological parameters repeated for another 2 weeks. At the end of the 1 month period of measurements for both groups of drivers, the Wait-list drivers will then receive a HEPA air purifier, so that they may also potentially benefit from the intervention being tested in this study, but no further measurements will be taken. Drivers will serve as their own controls before/after work and before and after the intervention.

Our taxi network CAB (Community Advisory/Action Board) will be engaged in the implementation and dissemination of the proposed study. This Taxi CAB represents the full range of the taxi driver experience, including varied shifts, income, education, age, ownership/lease arrangements, and countries of origin. The Taxi CAB will be instrumental in study recruitment and dissemination of results. The CAB will meet quarterly, with additional meetings as needed. This study is conducted in collaboration with Drs. [name] and [name]'s research teams at New York University Department of Environmental Medicine, and [name], working from the City College of New York (CCNY). Biological specimens collected will be immediately transported to MSK BAIC Core facilities for temporary storage and will be shipped later to either NYU or CCNY (outlined in the assessment and evaluation-section 7).

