5. **Serum cytokines and white blood cell profiles** (measured before and after work shift 1 work-day per week on week 1 and week 4): Serum cytokines (i.e., interleukin (IL)-1 β , -6, -8, -10, tumor necrosis factor (TNF)- α , and interferon (IFN)- γ) will be measured using dried blood spot sampling and MesoScale Discovery (MSD) immunoassay system (www.mesoscale.com). As done previously in collaboration with the EPA, a drop of blood will be spotted onto a commercial sampling paper and allowed to dry. The sampling paper will be labeled with study ID, date, and the initials of the person conducting the collection. The paper, along with other study samples, will be transported immediately to the BAIC Core facilities, 4th floor storage at -80 Freezer, until shipped on ice to our EPA collaborator, , for analyses. Blood samples for testing

will be obtained by punching a disc from the center of the spot, followed by a simple liquid extraction of the sample. MSD assays employ a sandwich immunoassay format whereby captured antibodies are coated in a single spot on the wells of a MULTI-SPOT plate. Multiplex assays can measure 1-10 cytokines in a 96-well MULTI SPOT plate; each sample will be analyzed in duplicate. A second blood drop from the finger stick will be placed onto a glass slide, air-dried, stored in a locked box for later H&E staining and used for differential counts of white blood cell profiles as a systemic marker of inflammation. Slides will be shipped to [name] at NYU for analysis. (See blood prick test procedures in appendix 4 for details).

6. **High sensitivity C-reactive protein *hs-CRP***: Similar to the processes described above, the blood sample for *hs-CRP* analysis will be a drop of blood spotted onto a commercial sampling paper and allowed to dry. The sampling paper will be labeled with study ID, date, and the initials of the person conducting the collection. The paper, along with other study samples, will be transported immediately to the BAIC Core facilities, 4th floor storage at -80 Freezer, for analyses. (See blood prick test procedures in appendix 4 for details).

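### The plan expects 25% drop-out but has no rule for a driver who leaves early; its 28-day PM summary can only exclude him or give him a truncated total

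*Combined protocol and SAP*

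**What the plan says.** Section 11.0 (Overview): "We plan to recruit a sample of n=14 participants in each group", followed by the projection "n=11 per arm with analyzable (non-missing) data, assuming a 25% drop-out rate as described below". The 25% is not mentioned again, so the promised description is missing. The same section states that "The general data analytic paradigm for this pilot study will be descriptive statistics only" and that the sample size was set mainly by resources.

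Section 11.0, Aim 1a: hourly PM readings become daily averages, and the AUC of the 28 daily averages is each driver's exposure summary. AUCs may be taken over time periods judged appropriate, but no window is fixed and no rule covers a driver with fewer than 28 days. Aim 1b gives, as an example, week-1 PM paired with week-1 cytokines.

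Section 11.0, Aim 2: the difference is taken "between the HEPA intervention condition and the Wait-List Control condition". No analysis set, time window, baseline adjustment or missing-data method is given.

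Section 10.0: "Participants may be removed from the study protocol based on the following circumstances", with four routes listed (withdrawal, ineligibility, distress, investigator's judgement). Nothing is said about data already collected.

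Section 7.1: PM is recorded daily and downloaded weekly, HRV is recorded daily, and blood pressure is taken on two days a week. Cytokines and white-cell profiles are "measured before and after work shift 1 work-day per week on week 1 and week 4". Urinary 1-hydroxypyrene is collected at the end of week 1 or 2 and at the end of week 4. Drop-out rates and reasons are recorded as feasibility data.

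Section 4.2: Intervention drivers get the filter after two weeks. After four weeks, "the Wait-list drivers will then receive a HEPA air purifier, so that they may also potentially benefit".

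**The concern.** The sizing sentence is the only place where the plan links leaving to the analysis, and there a leaver is counted as having no analysable data. For the frequently recorded measures that is not so. A driver who leaves in week 3 has a complete usual-conditions period and some data after day 14.

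Two things are at stake. For Aims 1a and 1b, valid pre-filter exposure data could be left out, and the summaries would then describe only drivers who tolerate the measurement burden. For Aim 2, a comparison of whoever finishes is no longer fully protected by randomisation if leaving is related to arm and exposure. Retention could differ by arm: after day 14 Intervention drivers already hold the purifier, while Wait-list drivers must finish to receive it. The Aim 2 estimate is meant to inform a larger trial.

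Without a rule, the choice between excluding leavers and truncating their totals would be made after the data are seen.

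**Working it through.** **1. The plan's own figure.** Inputs from Section 11.0: 14 per arm, 25% drop-out.
- 14 × (1 − 0.25) = 10.5, stated as 11. The figure reproduces after rounding up.
- Over both arms: 28 × 0.25 = 7 leavers, or 28 − 22 = 6 if 11 per arm is taken literally (3/14 = 21.4% loss).
- No power, effect size or SD is stated, so there is no power calculation to reproduce.

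**2. A leaver kept in the 28-day AUC.** At constant concentration, the truncated AUC as a share of the full one is days observed / 28.
- Leaves after day 7: 7/28 = 25%
- After day 14: 14/28 = 50%
- After day 21: 21/28 = 75%

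The shortfall reflects time on study, not exposure.

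**3. A leaver excluded.** With 3 leavers per arm, observed driver-days lost per arm = 3 × day of leaving. As a share of all observed days, this is 3 × day / (11 × 28 + 3 × day).
- Day 7: 21/329 = 6%
- Day 14: 42/350 = 12%
- Day 21: 63/371 = 17%

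**4. Precision of pre-filter summaries (Aims 1a and 1b).** The SE of a mean scales as 1/√n.
- All 28 drivers against 22 completers: √(22/28) = 0.886, an 11% smaller SE
- All 28 against 21 completers: √(21/28) = 0.866, a 13% smaller SE

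This is a ceiling, because it requires every leaver to finish weeks 1-2 and the documents give no drop-out timing.

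**5. Possible bias in Aim 2 from unequal drop-out.** Assume that leavers differ from stayers by k SD, in the same direction in both arms, with k from 0.25 to 1.0 (an assumption). With dI and dC leavers per arm, bias ≈ k × (dI − dC)/14.

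| Leavers, filter/control | Bias (SD) |
|---|---|
| 3/3 | 0 |
| 4/2 | 0.04 to 0.14 |
| 5/1 | 0.07 to 0.29 |
| 6/0 | 0.11 to 0.43 |

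The SE of the difference is 0.43 to 0.44 SD in all four rows.

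**6. Illustration of exposure-related drop-out.** Assumptions, none from the documents: 14 per arm; log PM with SD 0.6; true filter effect −0.5; filter-arm drop-out with logit −1.35 + 1.2 × baseline z (about 25% overall); control drop-out 25% at random; 20,000 simulated trials per setting.

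| Pre/post correlation | Completers, unadjusted (SD) | Completers, baseline-adjusted (SD) |
|---|---|---|
| 0.4 | −0.56 (0.27) | −0.50 (0.25) |
| 0.6 | −0.59 (0.26) | −0.50 (0.22) |
| 0.8 | −0.62 (0.26) | −0.50 (0.17) |

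The unadjusted difference overstates the effect by 0.06/0.50 = 12% up to 0.12/0.50 = 24%. Adjustment for the driver's own baseline removes this even when every leaver is excluded. With random drop-out in both arms the unadjusted difference is unbiased. The simulation contains no week-3 data, so it says nothing about the gain from recovering them.

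**7. What a leaver can supply.** PM, HRV and blood pressure exist for weeks 1-2 and for as much of week 3 as he stays. For cytokines, white cells and 1-hydroxypyrene, a driver who leaves before week 4 has no second value, and no analysis rule can recover one.

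**The case against.** The strongest reply is that the quoted sentence is a recruitment projection and not an analysis rule. A reader might infer from it that leavers are to be dropped and that Aim 2 is a completers' comparison. The documents do not support that reading: no section orders data discarded or restricts analysis to completers. Some text points the other way. PM files are downloaded weekly, AUCs may use other time periods, week-1 PM may be paired with week-1 cytokines, and Section 4.2 describes drivers as their own controls. This part of the reply stands, and the point is therefore a missing rule, not a wrong one.

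A reader might also take the 12-24% as the cost of losing leavers. It is not. It comes from an unadjusted post-filter comparison under an assumed drop-out pattern confined to the filter arm, and baseline adjustment among completers already cures it. Nor do the documents show that drop-out will differ by arm: the purifier's timing makes this plausible, but the weekly cash payment is the same in both arms.

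Finally, this is a descriptive pilot sized by resources, so an elaborate model would be out of proportion. That is fair, and it limits the remedy. It does not excuse leaving the analysis set undefined, since the latitude over time periods does not say how a driver with fewer than 28 days is scored.

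**Conclusion.** The point holds as a gap in the plan. As written, the 28-day AUC offers two ways of handling an early leaver, exclusion or a truncated total, and neither is acceptable: the second scores him at 25% to 75% of his full-period value for leaving after day 7 to day 21 at constant exposure. Aim 2 has no analysis set, window or baseline adjustment, and the 25% has no stated basis.

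The measurable gain from using all weeks 1-2 data is at most an 11-13% smaller SE for pre-filter summaries. Bias in Aim 2 ranges from none (equal drop-out with leavers alike in both arms, or random drop-out) to 0.43 SD in the extreme assumed split, against an SE of about 0.43 to 0.44 SD. The documents do not allow a choice within that range. The consequence is a possibly biased and less precise pilot estimate, not an invalid confirmatory result. The change is worth making because it is cheap and the estimate is meant to guide a larger study.

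**What to change.** In Section 11.0:

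1. **Analysis set and PM summary.** State that every randomised driver with any data in a window is analysed in his assigned arm. Define PM as the mean per observed day, separately for weeks 1-2 and weeks 3-4, with a minimum-days rule for each window. Aims 1a and 1b then use all drivers' weeks 1-2 data, whether or not they finish.
2. **Aim 2 for PM, HRV and blood pressure.** Estimate the weeks 3-4 difference between arms adjusted for the driver's own weeks 1-2 value, by ANCOVA or a simple repeated-measures model with a common pre-filter mean. Include leavers' data after day 14, and show completers only as a sensitivity analysis.
3. **Drop-out.** Under Aim 3, report drop-out by arm and by before or after day 14. Give the basis for the 25%, or delete the reference to a description.

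The cost is a few sentences and a standard analysis, with no added participants, visits or procedures; no exit sampling is proposed. Two limits remain. The analysis assumes that drop-out is missing at random given the observed data, and leavers contribute fewer filter days than drivers who finish.

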2.0 OBJECTIVES AND SCIENTIFIC AIMS

1a) To collect preliminary data on in-vehicle excess PM exposure, including size distribution, mass concentration, and chemical composition among taxi drivers (measured during work shifts and at home).

1b) To conduct a preliminary assessment of the correlation between PM exposure and physiologic and biochemical markers associated with increased risk of lung cancer and/or CVD. Physiologic and biochemical markers will include pro/anti-inflammatory cytokines, epigenetic changes (associated with cancer and/or inflammation), and high-sensitivity C-reactive protein, blood pressure, and reduced heart rate variability (associated with CVD).

2) To use a randomized wait-list controlled design to conduct a pilot study of whether a targeted intervention, installation of a portable car high-efficiency particulate air (HEPA) filter (to remove PM), results in a reduction of in-vehicle PM exposure and associated physiologic and biochemical markers among taxi drivers.

3) To collect data on the feasibility of conducting a larger RO-1 type (NIH granting mechanism) randomized wait-list controlled pilot study among New York City taxi drivers.

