3.0 BACKGROUND AND RATIONALE

There are approximately 240,000 taxi/limousine drivers in the U.S. (1). By 2020, this number is expected to increase by 20% (1). New York City (NYC) is home to 100,000 taxi drivers, among whom 92% are immigrants (2, 155). Forty percent of those are South Asian (originating from India, Pakistan, Bangladesh, Nepal, and Sri Lanka) (2), followed by large numbers of drivers from the Dominican Republic, Mexico, former USSR, Haiti, Nigeria, Ethiopia, Columbia, Ecuador, and Jamaica (2). The overwhelming majority of taxi drivers are minority men. They are at great risk for increased cancer risk and poor cardiovascular health due to a number of occupation-related factors, including stress, diet, sedentary lifestyle, and poor health care access (18-21).

They work long hours (10-12 h/d shifts, ~6d/wk (2)), most often in heavy traffic, and are exposed to environmental contaminants. This exposure, including to ambient particulate matter (PM) (even low-level exposure to fine airborne PM [PM smaller than 2.5 micrometers (PM_{2.5})]), increases health risk (13, 22, 23). Even short-term exposure (i.e., while driving) to peak particle concentrations appears to be linked with adverse health effects (24-27). A vehicle cabin is a relatively confined space where drivers are exposed to high concentrations of PM. In comparison to outdoor/indoor microenvironments, in-vehicle PM levels are often very high, originate from external sources, including road traffic (28), and can be 3-5 times that of outdoor PM values (29). In a study examining PM levels in private cars, values in moving vehicles exceeded those in parked cars by 9.2 times for PM₁₀ (PM smaller than 10 micrometers) and 3.8 times for PM_{2.5} (28). These conditions can potentially be improved at very low cost, with a HEPA filter, with a resultant diminution of lung cancer and cardiovascular disease (CVD) risk in this vulnerable group of minority men.

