
experience. Thirty-four percent of respondents stated they were —not worriedll about being exposed to air pollution while driving, while another 40% said they were —a little or somewhat worriedll. Nineteen percent reported that they believed they had a health problem attributable to air pollution exposure. In [name] protocol X12-021, a pilot investigation of particulate matter concentrations in NYC taxi cabs, we measured levels of in-vehicle Particulate Matter (PM) concentration in a convenience sample of 7 NYC Taxi Cabs. In-vehicle PM levels were measured through *Personal DataRams*(pDR) and *Microaethalometers*, which were placed on the passenger seat or console area of the taxicab for the full 6-hour shift. Near-roadway outdoor air monitoring of PM and BC concentrations was also conducted using aerosol monitors. Compared with previously published results of personal exposure studies conducted in NYC (156, 157), taxicab PM and BC concentrations were elevated. Average concentrations of PM per 15-minute interval for all seven shifts indicated large intra- and inter-car variability. Per shift average PM concentrations ranged from 4 $\mu\text{g}/\text{m}^3$ to 49 $\mu\text{g}/\text{m}^3$ and 1-minute peak levels measured up to 452 $\mu\text{g}/\text{m}^3$. Black carbon levels were also elevated, and reached over 10 $\mu\text{g}/\text{m}^3$. Peak in-vehicle PM levels were short and sporadic, and may have been influenced by external events, such as passenger smoking, as recalled by drivers after their shift. Roadside air monitoring was conducted at three large taxi passenger pick-up stands in midtown Manhattan, all located at traffic hubs and mass transport terminals. Monitoring during morning and evening rush hours revealed ambient PM levels to be near or greater than the EPA 24 hour NAAQS of 35 $\mu\text{g}/\text{m}^3$ for $\text{PM}_{2.5}$. Average levels at each taxi stand were 44 $\mu\text{g}/\text{m}^3$ (SD \pm 32), 58 $\mu\text{g}/\text{m}^3$ (SD \pm 10), and 76 $\mu\text{g}/\text{m}^3$, (SD \pm 43) and peak levels were as high as 434 $\mu\text{g}/\text{m}^3$, mirroring peak in-vehicle values. Levels of black carbon were also found to be high; peak levels at one taxi stand were as high as 12 $\mu\text{g}/\text{m}^3$. Average taxi stand BC and PM levels were significantly higher than levels recorded at the closest New York State Department of Environmental Conservation's air monitoring site (Division Street) (158). As a sedentary occupational group with a disproportionate prevalence of disease, taxi drivers are likely at greater risk from air pollutant exposure than those working away from roadways. Community-engaged interventions are needed to limit their exposure to high levels of PM and BC. The proposed DRIIVE project will move the preliminary data a step forward and the CAB will continue to play a central role in planning, implementation, and dissemination.

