4.3 Intervention

Over the course of the study, we will monitor several biological and physiological markers associated with lung cancer and CVD risk, along with ongoing air monitoring of work-sites and residences of all study participants. HEPA filters were selected as the intervention because of their effectiveness in removing PM and volatile organic compounds (VOCs), ease of use, relatively low-cost, small size, light weight, and lack of interference with drivers' normal practices (136). In a previous study by Pui et al., placing the air recirculation mode on (and with a cabin air filter in place already installed by the car manufacturer, not all cars have cabin air filters), was successful at substantially removing ultrafine particles, although was still relatively inefficient (45.5% particle removal efficiency) compared to a HEPA filter (137).

The study will require 4 weeks of participation. Drivers will be recruited and randomized to either the control condition or the HEPA filter intervention condition. The in-vehicle (for all drivers PM exposure levels and physiologic and biochemical markers will be measured over the course of 1 month. For the first two weeks of the 1-month period, measurements will be taken under usual conditions (*without HEPA filters*) for all participants.

Particulate matter concentrations will be measured/monitored through *Personal DataRams* (pDR) (*personalDataRam*[™] model pDR-1200). The DataRam measures particulate matter through optical impedance, and produces per-minute averages. Therefore, the time that the DataRam is —onll will be directly reflected in the data that is produced. The pDR is 24 ounces, 6.3 inches in height, 8.1 inches in width, and 2.4 inches in depth, and is thus very portable. One pDR will be provided to each enrolled participant. All participants will monitor PM at their homes in the room in which they spend most of their off work hours; the DataRam will then be moved to the bedroom at night (or during sleeping hours). For drivers, the pDR will record PM levels throughout the work shift while the vehicle is in motion, momentarily stopped, or parked.

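### The only worked PM summary in Section 11 does not separate cab from home, so it cannot give in-vehicle PM or its excess, the first primary outcome

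*Combined protocol and SAP*

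**What the plan says.** Section 11.0 gives in-vehicle excess PM as the target of Aim 1a, and Section 9.1 lists it as the first primary outcome. Section 9.1 ties it to DataRam readings ("hourly averages) that will be monitored at work site and at homes across all groups"). Objective 1a in Section 2.0 likewise has PM, including its "chemical composition among taxi drivers (measured during work shifts and at home").

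Section 4.3 gives each participant one DataRam. It records in the cab throughout the shift. Off shift, "All participants will monitor PM at their homes in the room in which they spend most of their off work hours", and it moves to the bedroom for sleep. Item 1 of Section 7.1 repeats this.

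For Aim 1a, Section 11.0 plans means and standard deviations by group, and a per-driver area under the curve (AUC) over time periods left to judgement. The one rule it works through takes a daily average of the hourly values. After that, "Then the AUC of the 28 daily averages will be calculated per person to represent the summary of PM exposures during study participation". Under Aim 1b it adds an example, a week-1 AUC matched to week-1 cytokines. For Aim 2 it plans a difference between the two conditions and gives no location, period or baseline for it.

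**The concern.** A reader who follows the worked rule gets one number per driver that blends shift hours, evenings, sleep and days off. That is a total-exposure measure. The primary quantity concerns one of the two places, and excess implies a contrast between them. Neither can be recovered from the blend.

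Two drivers could have the same summary while one breathes dirtier air in the cab and the other at home. For Intervention drivers the number also combines two weeks without the filter and two weeks with it, so it does not describe usual in-cab conditions either. The pilot's stated purpose is to guide a larger randomized trial. An in-vehicle figure taken from this summary would mislead that planning.

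**Working it through.** **Plan's own figures.** Section 11.0 has no power calculation or expected PM value to reproduce. Its one derived figure is 11 analysable drivers per arm: 14 × (1 − 0.25) = 10.5, rounded up. It plays no part here.

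**Inputs from the documents.** Shifts are 10-12 h on about 6 days a week (Sections 1.0 and 3.0). The study period is 28 days (footnote to the schedule in Section 7.1). There is one DataRam per driver (Section 4.3). The filter is installed after two weeks in the Intervention arm (Section 4.2).

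**Assumption.** The device records round the clock.

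**Days.** 28 × 6/7 = 24 work days, which leaves 4 days off. At least those 4 daily averages contain no shift hours, so the 28 values cannot all be in-vehicle.

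**Cab share of the summary.** The total is 28 × 24 = 672 h.
- 10 h shifts: 24 × 10 = 240 h; 240/672 = 35.7%.
- 12 h shifts: 24 × 12 = 288 h; 288/672 = 42.9%.

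The remaining 57-64% is off shift, mostly at home.

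**Filter mixing.** For an Intervention driver, 12 of the 24 work days fall in weeks 3-4. Half of the cab hours (120 of 240, or 144 of 288) are therefore in the filtered period.

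**What the blend hides.** With cab share f, the 28-day mean is f × cab + (1 − f) × home. The levels below are assumed for illustration, in µg/m³.

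| Shift | Driver | Cab | Home | 28-day mean | Cab minus home |
|---|---|---|---|---|---|
| 10 h | A | 28 | 10 | 0.357 × 28 + 0.643 × 10 = 16.4 | +18 |
| 10 h | B | 10 | 20 | 0.357 × 10 + 0.643 × 20 = 16.4 | −10 |
| 12 h | A | 28 | 10 | 0.429 × 28 + 0.571 × 10 = 17.7 | +18 |
| 12 h | B | 10 | 23.5 | 0.429 × 10 + 0.571 × 23.5 = 17.7 | −13.5 |

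At 10 h, driver A's work-day average is (10 × 28 + 14 × 10)/24 = 17.5, with 10 on days off. Driver B's is (10 × 10 + 14 × 20)/24 = 15.83, with 20 on days off. Over 28 days:
- A: 24 × 17.5 + 4 × 10 = 460 µg/m³-days.
- B: 24 × 15.83 + 4 × 20 = 460 µg/m³-days.

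A trapezoid AUC that starts on a work day and ends on a day off subtracts half of the first and last values:
- A: 460 − (17.5 + 10)/2 = 446.
- B: 460 − (15.83 + 20)/2 = 442.

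The sums are identical and the trapezoid values differ by about 1%, while the cab-minus-home differences have opposite signs.

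**Other text in Section 11.0.** The means and standard deviations by group, the freedom over time periods and the week-1 example each allow another window or statistic. None restricts the hours to the cab, and none subtracts a reference.

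**The case against.** The strongest reply is that pooling is inferred rather than written. Section 11.0 softens the rule, leaves the time periods open and labels the result a summary of exposure during participation. Aim 1b then uses it in a role where it is acceptable. All of that is fair, and it is why the AUC should stay for Aim 1b. But no other calculation is offered for the primary quantity, and 28 daily averages that include days off cannot be in-vehicle values.

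A second reply is that this is a descriptive pilot and that time stamps, the log-book or laboratory documents not shown here would let an analyst make the split. That probably makes the fault repairable. It does not put the calculation into the plan, where time stamps are mentioned only for matching PM to biomarkers.

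The two-driver example is constructed, and it needs home PM above cab PM. It shows what the summary cannot distinguish, not what is likely.

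Four stronger readings are tempting but not supported:
- *Excess has no reference, so its sign is open.* Section 3.0 does set cab PM beside outdoor air ("and can be 3-5 times that of outdoor PM values (29") and published personal exposures ("Compared with previously published results of personal exposure studies conducted in NYC (156, 157), taxicab PM and BC concentrations were elevated"). That is background and preliminary work and does not define this trial's outcome. Sections 2.0 and 9.1 point to home. What is missing is the stated contrast.
- *The 28-day summary would dilute the Aim 2 filter effect.* The text does not say that Aim 2 uses that summary, and Aim 2 names in-vehicle PM.
- *The rule cannot be applied to chemical composition.* The daily step is described for hourly values and need not reach filter samples. At most this is a wording clarification.
- *Hourly files blur a known share of each shift.* The documents do not say how the hours are aligned to shifts.

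**Conclusion.** The point stands and should be fixed. The plan names in-vehicle excess PM as its first primary quantity and writes out no calculation that produces it. The one worked summary is about 36-43% cab time, includes about 4 days off, and mixes filtered and unfiltered weeks in the Intervention arm.

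The percentages rest on round-the-clock recording and on a shift pattern that the protocol gives as background for New York drivers, not as a study requirement. Incomplete home recording would raise the cab share and make it vary between drivers. The structural conclusion does not depend on these figures. The fault lies in the written analysis rule, not in data collection, and the data to be collected should allow the correct calculation.

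**What to change.** 1. State that excess means in-vehicle minus home PM, the reading that Sections 2.0 and 9.1 best support.
2. Classify DataRam readings as cab or home from device time stamps and the log-book. The log-book contents listed in Section 7.1 do not mention shift times, and Appendix C is not shown. If start and end times are absent, add them. Section 4.3 says "The DataRam measures particulate matter through optical impedance, and produces per-minute averages", whereas Section 7.1 describes hourly files. Keeping the finer data, if the download allows it, makes the classification cleaner.
3. For each driver, report time-weighted mean PM mass in-vehicle and at home, separately for weeks 1-2 and weeks 3-4. Take Aim 1a from unfiltered time only: weeks 1-2 in both arms, and weeks 3-4 in controls.
4. For Aim 2, report descriptively the between-arm difference in weeks 3-4 in-vehicle PM, adjusted for, or as change from, the driver's own weeks 1-2 in-vehicle mean. This uses the own-control feature in Section 4.2.
5. Keep the all-hours AUC for Aim 1b only, with the time matching already planned there.

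The cost is plan wording, data handling and possibly added log-book fields for shift times, with no new visits or samples. The downside is that some readings will be misclassified or left out where logs are incomplete.
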